Patients requiring a dose delay of > 28 days must be permanently discontinued from study drug. Following 4 cycles of therapy for responding patients (i.e. CR, PR, HI, or marrow CR), treatment with APR-246 and azacitidine can be delayed per the study investigator for up to 14 days to allow for count recovery or at investigator discretion post discussion with Moffitt PI. Non-hematologic grade 4 treatment related adverse events will lead to permanent discontinuation, irrespective of recovery time, unless otherwise specified. Exceptions would include nausea/vomiting/diarrhea which can be controlled by medications and/or asymptomatic electrolyte imbalances which can be corrected. In addition, in most instances, patients that experience a prolonged treatment interruption because of an adverse event and/or a grade 3 adverse event will decrease the dose of study drug after their recovery (see specific tables for dose adjustment guidelines). Furthermore, patients requiring >1 dose reduction for APR-246 will be permanently discontinued from study drug. Patients who permanently discontinue all study drugs should have follow-up within 30 days after discontinuation of all study treatment or resolution of the AE to \leq grade 1, whichever occurs first, that includes all study assessments appropriate to monitor the event.

4. DLT Definition

Patients will be evaluated for DLTs during the lead-in phase and first cycle of combination therapy, i.e., 6 weeks for purpose of deciding the dose for next cohort (see Table 1) but DLTs will continue to be evaluated and reported through all cycles on study. DLT is defined as follows based on the CTCAE v 4.03:

- Treatment related non-hematological CTCAE grade 3-4 toxicity that lead to dose modification or withdrawal.
- Absolute neutrophil count (ANC) not recovering to $>500/\mu\text{L}$ by day 42 of a cycle in the absence of active leukemia/myelodysplasia will be considered a DLT.
- Grade 3 metabolic/electrolyte abnormalities that are not clinically significant, and are adequately controlled within 72 hours are not to be considered DLT.
- Grade 3 nausea/vomiting/diarrhea or CNS toxicity that does not resolve within 28 days despite treatment interruption and maximum medical therapy will be considered a DLT.

5. Criteria for APR-246 dose modifications (Phase 2)

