Events that **do not** meet the definition of an AE include:

- Medical or surgical procedure (e.g., endoscopy, appendectomy); the condition that leads to the procedure is either an AE or (if existing pre-study) a baseline medical history item.
- Situations where an untoward medical occurrence did not occur (social and/or convenience admission to a hospital. Example: Hospital admission for sole purpose of red blood cell transfusion).
- Anticipated day-to-day fluctuations of pre-existing disease(s) or condition(s) present or detected at the start of the study that do not worsen.
- Signs/symptoms of Gr. 1 or Gr. 2 expected side effects of Azacitidine, as noted in visit notes by treating MD and/or designated staff. This includes (for example, but not limited to) Gr. 1-2: Nausea, constipation, injection site reactions, decreased neutrophil count, decreased platelet count. Must be located in source document that items are specifically attributable to Azacitidine.

- Signs/symptoms of Gr. 1 or Gr. 2 expected side effects of red blood cell and/or platelet transfusion needs. This includes (for example, but not limited to) Gr. 1-2: dizziness, headache, hypotension, hypertension, dyspnea, muscle weakness, ataxia, fall, petechiae, bruising. Must be located in source document that items are specifically attributable to the need for red blood cell transfusion and/or platelet transfusion.
- Items which are transient (example: seasonal allergies; joint pain during thunderstorms) will be listed as baseline medical history items and are not considered new AEs if only occurring during certain times of year or with certain events if ongoing chronically, and do not increase in grade and are not attributable to study medication.

b. Serious Adverse Event (SAE) Definition

A serious adverse event is one that at any dose (including overdose):

- Results in death
- Is life-threatening
- Requires inpatient hospitalization or prolongation of existing hospitalization
- Results in persistent or significant disability or incapacity
- Is a congenital anomaly or birth defect
- Is an important medical event
- Suspected positive pregnancy

NOTE: The term “life-threatening” the definition refers to an event in which the subject was at risk of death at the time of the event. It does not refer to an event, which hypothetically might have caused death, if it were more severe.

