It is a regulatory requirement for investigators to assess relationship to investigational product based on information available. The assessment should be reviewed on receipt of any new information and amended if necessary. "A reasonable possibility" is meant to convey that there are facts/evidence or arguments to suggest a causal relationship. Facts/evidence or arguments that may support "a reasonable possibility" include, e.g., a temporal relationship, a pharmacologically-predicted event, or positive dechallenge or rechallenge. Confounding factors, such as concomitant medication, a concurrent illness, or relevant medical history, should also be considered.

d. Laboratory and Other Safety Assessment Abnormalities Reported as AEs and SAEs

Any abnormal laboratory test results (hematology, clinical chemistry, or urinalysis) or other safety assessments (e.g., ECGs, vital signs measurements), including those that worsen from baseline should be recorded as per the NCI-CTCAE 4.03 criteria. However, these laboratory results are to be recorded as AEs or SAEs if deemed clinically significant in the medical and scientific judgment of the investigator or treating physician. Any clinically significant safety

assessments that are associated with the underlying disease are **not** to be reported as AEs or SAEs, except for findings judged by the investigator or treating physician to be more severe than expected for the subject's condition or death. Data will be collected for typical disease-related events such as anemia, leukopenia or worsening of thrombocytopenia. All infections experienced during the study are to be recorded as AEs or SAEs.

e. Disease-Related Events and/or Disease-Related Outcomes Not Qualifying as SAEs

During the study period, the following conditions will not qualify as an AE or SAE provided they are not considered attributable to study medication:

- Events that occur prior to the 1st dose of APR-246.
- Cases of disease progression.

f. Pregnancy

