Stage 2: Enroll 21 more evaluable patients for a total of 45. If less than 14 of 45 patients achieve CR, then there is insufficient evidence to support continued study of this treatment. If at least 14 of 45 patients achieve CR, then there is sufficient evidence to support further study of APR-246 in combination with azacitidine in Phase 3. Up to 39 additional evaluable patients will be treated at the level of the MTD in the

Phase 2 portion of the trial.

This rule has the following operating characteristics: 90% power, with $\alpha=0.05$ under the null hypothesis that the proportion of patients achieving CR is $\leq 20\%$ versus the alternative hypothesis that it is $\geq 40\%$. This design has a probability of early termination equal to 0.66 if the true CR rate is 20%.

2. Statistical Analysis Methods

Demographic and clinical variables for the study patients will be summarized using descriptive statistics (mean, standard deviation, median, inter-quartile range, range, frequency counts and percentages). Safety and efficacy data will be analyzed overall as well as separately for each dose cohort when appropriate.

3. Safety Analysis

This analysis will include all subjects who have received any protocol treatment, regardless of patient eligibility. The number (%) of subjects with adverse events, serious adverse events, and adverse events leading to treatment discontinuation will be reported. Adverse events summary will be reported by type and severity. Laboratory parameters will also be summarized using descriptive statistics.

4. Efficacy Analysis: ITT

This analysis will include all subjects who have received any protocol treatment, regardless of patient eligibility or duration of treatment. Those who have no response assessment data due to reasons such as drop out of the study, withdrawal consent, or lost to follow-up will be treated as non-responders for various response evaluations. The proportion of subjects achieving the primary endpoint will be summarized. A 95% exact binomial confidence interval of the proportion will also be provided for all participants treated at the MTD. In addition, a second analysis of evaluable subjects will be performed. Evaluable subjects are defined as those who complete at least 3 cycles of therapy and complete the first on treatment bone marrow biopsy and aspirate to evaluate study drug response.

Analyses of the following secondary endpoints will be performed as well:

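### The reported rate of grade 3-4 cytopenia depends on investigator attribution, and no grade table based on the blood counts is planned beside it

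*Combined protocol and SAP*

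**What the plan says.** **What becomes an AE.** Under Section 11.d a laboratory abnormality is an AE or SAE only if the investigator or treating physician finds it clinically significant. A second rule then applies to the significant ones: "assessments that are associated with the underlying disease are not to be reported as AEs or SAEs". Death is exempt from this second rule. So is a finding that passes a severity test, worded as "except for findings judged by the investigator or treating physician to be more severe than expected" and measured against the individual patient. No threshold or baseline reference is given for what is expected.

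**What is still collected.** The same section says: "Data will be collected for typical disease-related events such as anemia, leukopenia or worsening of thrombocytopenia". Laboratory abnormalities, "including those that worsen from baseline should be recorded as per the NCI-CTCAE 4.03 criteria", are to be recorded whether or not they become AEs.

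**Azacitidine effects.** Section 11.a lists events that are not AEs, among them "Signs/symptoms of Gr. 1 or Gr. 2 expected side effects of Azacitidine", with these examples: "Nausea, constipation, injection site reactions, decreased neutrophil count, decreased platelet count".

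**DLT.** The one hematologic criterion in Section 10.4 is neutrophil non-recovery "by day 42 of a cycle in the absence of active leukemia/myelodysplasia will be considered a DLT".

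**Analysis.** Section 15.3 reports numbers and percentages of subjects with AEs, SAEs and AEs leading to discontinuation, and AEs by type and severity. For laboratory data it adds one sentence: "Laboratory parameters will also be summarized using descriptive statistics".

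**The concern.** Low neutrophils, platelets and hemoglobin are features of the diseases enrolled. The protocol also treats low neutrophils and platelets as possible treatment effects: there is a neutrophil DLT, Table 8 has neutropenia and thrombocytopenia rows, and Section 11.a calls neutrophil and platelet decreases expected effects of azacitidine. When a count falls on treatment, someone must decide whether disease or drug is responsible. There is no control arm and no blinding to help with that decision.

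The AE tables inherit it. Two sites with identical blood counts could report different rates of grade 3-4 cytopenia, and nothing else specified in Section 15.3 would show it. The rate will be read beside the efficacy result, so it should have a version that does not rest on attribution.

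**Working it through.** The plan states no cytopenia rate, so there is no figure to reproduce. The check is mainly a reading of the rules.

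**Step 1. The AE route.** Take a platelet count that worsens to grade 3 or 4 on treatment. To reach the Section 15.3 tables under Section 11.d it must be judged clinically significant. It must then be judged either not associated with the disease or more severe than expected for that subject. Each step is a judgement. These steps can take a recorded worsening out of the AE tables but cannot add one.

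**Step 2. The other hematologic routes.** Each is conditional:
- The DLT covers neutrophils only, and not when disease is active. It is reported through all cycles.
- The hematologic rows of Table 8 apply only to patients with normal baseline neutrophils and platelets.
- The grade 4 laboratory abnormalities listed among the SAE criteria in Section 11.b are non-hematologic.
- The internal safety review in Section 17.8 lists AEs of grade 3 or above, so a cytopenia not entered as an AE is not on that list.

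**Step 3. How far the rate could move.** Let w be the proportion of patients who worsen to grade 3-4 on treatment from any cause. Let a be the share of those patients whose worsening is not entered as an AE because it is judged an expected disease finding. Then

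reported rate = w × (1 − a).

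Neither w nor a is in the documents. The values below are assumptions that show the range.

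| w | a = 0 | a = 25% | a = 50% | a = 75% |
|---|---|---|---|---|
| 30% | 30% | 22.5% | 15% | 7.5% |
| 50% | 50% | 37.5% | 25% | 12.5% |
| 70% | 70% | 52.5% | 35% | 17.5% |

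For example, 50% × (1 − 0.50) = 25%. The table shows sensitivity to a and does not estimate it.

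**Step 4. Would descriptive count summaries reveal it?** Assume 45 patients with a 40% response rate: 18 gain 60 × 10⁹/L platelets and 27 lose 30.
- Mean change = (18 × 60 − 27 × 30)/45 = (1080 − 810)/45 = +6.
- Median change = −30, because 27 of 45 patients have that value.

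The mean hides the worsening; the median shows it. Now suppose 13 of the 27 have left, so 18 + 14 = 32 remain.
- Mean = (1080 − 14 × 30)/32 = 660/32 = +20.6.
- Median = +60.
- Lower quartile = −30.

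Whether a summary shows the worsening therefore depends on which statistics are chosen and who is still on treatment, and Section 15.3 fixes neither.

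**Step 5. When the count schedule is comparable.** The notes to the study calendar let patients in CR or PR after cycle 3 have required counts on Day 1 of each later cycle only. Before that assessment the schedule does not depend on response. The calendar table is damaged in extraction and appears to show a Day 22 count in cycle 1 only, so the schedule should not be called weekly throughout cycles 1-3.

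**The case against.** The strongest reply is that the protocol has more safeguards than Section 11.d alone suggests.

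- The exclusion is not absolute: findings more severe than expected for the subject remain reportable.
- Section 11.a counts an exacerbation of a pre-existing condition as an AE and exempts only anticipated fluctuations that do not worsen. Its azacitidine exemption stops at grade 2, so it does not touch grade 3-4 events.
- Section 11.c accepts timing and pharmacological prediction as support for drug causality, which a count fall after azacitidine could meet.
- All infections are AEs or SAEs, and Section 11.g asks for SAEs whether or not related.
- A transfusion log runs to end of treatment.
- Section 15.2 lists medians, inter-quartile ranges, frequency counts and percentages among its descriptive statistics, so a grade table would be consistent with the plan.

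All of this stands, and it rules out several stronger readings:

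- A reader might infer that disease-attributed grade 3-4 cytopenias can never enter the AE tables. The exception in Section 11.d and the exacerbation rule in Section 11.a say otherwise.
- A reader might infer that the rate is understated by a known amount. The documents give neither the true rate nor the share set aside.
- A reader might infer that recovering responders will conceal toxicity. Step 4 shows this is certain only for the mean of that example.
- A reader might infer that marrow suppression is the main overlapping toxicity and drives the Phase 3 decision. The clinical AE detail for APR-246 is redacted, and the stated criterion for further study is at least 14 CRs in 45 patients.

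The safeguards leave one gap. They govern what may be recorded, and they point in different directions. None commits the analysis to a cytopenia rate that is independent of attribution. The descriptive list in Section 15.2 is written for demographic and clinical variables, and Section 15.3 names no grade, nadir or change from baseline.

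**Conclusion.** The point holds as a gap in the planned safety analysis. The reported rate of grade 3-4 cytopenia depends on open-label attribution in a single-arm trial and may be lower than the rate of worsening in the recorded counts. How much lower cannot be derived; the Step 3 range, from no loss to a loss of three quarters, reflects only the assumed share set aside.

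The comparison is with worsening from any cause. The documents do not allow drug-caused worsening to be separated from disease-caused worsening, so no claim is made about the rate due to the combination itself. The primary endpoint, sample size and stopping boundaries are unaffected. Because the graded counts are collected, the gap can be closed in the analysis plan, and this is worth doing as an inexpensive improvement.

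**What to change.** Add to Section 15.3 wording such as:

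> For neutrophils, platelets and hemoglobin, baseline CTCAE grade will be cross-tabulated with worst on-treatment grade from the recorded blood counts, regardless of AE reporting or attribution. The table will be given overall, for cycles 1-3, and by dose level. The proportion worsening to grade 3-4 will be reported among patients with baseline grade 0-2, and the proportion worsening to grade 4 among patients with baseline grade 0-3, each with an exact 95% confidence interval.

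Three details complete it:

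- Define baseline and the on-treatment window, including whether the Phase 1b lead-in counts. State how a grade is assigned where the laboratory value alone does not settle it.
- Present the table beside the AE table, not in its place, with a footnote that it includes worsening caused by the disease.
- State the number in each denominator. Patients who start at a high grade cannot contribute, and the documents give no baseline distribution from which to predict how many remain.

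Separately, the sponsor should reconcile Section 11.a (exacerbations are AEs), Section 11.d (disease-associated findings are not AEs or SAEs, with exceptions) and Section 11.g (SAEs reported whether or not related), so that sites apply one rule. Which rule to adopt is the sponsor's decision.

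The cost is one paragraph of analysis text and one table from counts already scheduled and graded, with no new visits or patients. The downside is a higher reported cytopenia rate that mixes disease and treatment effects, which is why the footnote is needed.

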12. PHARMACEUTICAL INFORMATION

a. Study Treatments and Preparation

[REDACTED]

[figure not shown]

Figure 3. Structure of APR-246

b. Study drug compliance and accountability

1. Study drug accountability

The investigator or designee must maintain an accurate record of the shipment and

dispensing of study treatment in a drug accountability ledger. At study close-out, and, as appropriate during the course of the study, the investigational pharmacy will destroy all used and unused study treatment, packaging, and drug labels per the MCC drug destruction policy.

2. Disposal and destruction

Study drug destruction at the investigational site will only be permitted if authorized by Aprea after the site's drug destruction policy has been reviewed and deemed acceptable and if permitted by local regulations.

13. Study Calendar

All screening evaluations will be performed within 4 weeks prior to the start of APR-246 and azacitidine treatment. Subjects must have a bone marrow biopsy and aspirate (including cytogenetics) performed sometime within 4 weeks prior to the start of treatment. All transfusion and pre-transfusion hemoglobin or platelet count must be recorded for the 8 weeks prior to initiation of study treatment. Strict adherence to the visit schedule is required. In the event that a visit or test cannot be scheduled on the exact visit day, a window of ± 7 working days is allowable. Tests (including bone marrow biopsies and aspirates) done within the screening period prior to signing informed consent are allowed for use in this study.

1. **Baseline Assessment**: within 4 weeks of starting treatment

Medical history including:

- Disease characteristics such as WHO/FAB subtype, R-IPSS score, prior treatments.
- ECOG performance status
- Concurrent medication review
- Routine physical examination
- EKG
- Bone marrow exam, including cytomorphology, cytogenetic assessment, and flow cytometry analysis
- Documentation of a *TP53* gene mutation by NGS based on central or local evaluation
- Laboratory assessments:
 - ▶ CBC with differential (including platelet count)
 - ▶ Clinical chemistries including BUN, creatinine, sodium, potassium, alkaline phosphatase, ALT, AST, total bilirubin and albumin

- ▶ Urine or serum pregnancy test for females of childbearing potential will be performed at Screening or on first day of study medication, prior to first dose of study medication
 - Record any blood and blood supportive care products for the 8 weeks prior to start of study medication.
2. **Treatment Period** (Day -14 - Cycle 6): APR-246 and azacitidine will be administered over a 28 day treatment cycle. Patients will have medical history, physical exam, performance status every 4 weeks. Subjects will have a CBC with differential (including platelet count) and a complete metabolic profile (CMP) performed. A BM aspirate and biopsy with cytogenetic analysis will be performed after cycle 3 and 6 (C3D22 and C6D22). An NGS myeloid panel will be performed on PB prior to cycle 1 and after cycle 3 and 6 (C3D22 and C6D22). If *TP53* mutation is only present on BM analysis at screening, serial NGS myeloid panel can be performed on bone marrow. These analyses will be used to assess pathologic response, cytogenetic response, molecular response and disease progression.
 3. **End of Treatment**: Subjects will complete a response assessment within 4 weeks after their last dose of APR-246 and azacitidine. Subjects discontinuing study early should complete their end of treatment visit within 4 weeks after their last dose of investigational product. Physical exam, vital signs, adverse event reporting, CBC, CMP and BM aspirate and biopsy with cytogenetic analysis will be performed. If end of treatment tests are declined or not feasible, not considered deviation.

Continuation Phase: After completing 6 cycles of therapy, subjects responding or who have stable disease may continue APR-246 and azacitidine. Bone marrow biopsy and aspirate will be repeated after every 3 cycles. An NGS myeloid panel should be performed on PB every 3 cycles. A CBC and CMP will be obtained every 4 weeks.

4. **End of treatment assessment**: includes best response achieved, date of first response, date of loss of response, reason for discontinuation.

Off treatment follow-up: include vital status, date of death/last contact, transformation to AML and the date of transformation to AML if applicable.

Study Calendar Evaluation*	Baseline/ Screening *	Lead-in phase***						Cycle 1						Cycle 2 and Subsequent Cycles					Every 3 Cycles	End of Treatment****
		Day -14	Day -13	Day -12	Day-11	Day -10	Day -7	Day 1	Day 2	Day 3	Day 4 ^a	Day 8	Day 15	Day 22	Prior to/Day 1 ^b	Days 1-4 ^a	Day 8	Day 15		
Informed consent	X																			
Baseline medical history ^c	X																			
Physical exam ^d	X	X						X							X					
Height	X																			
Weight	X	X						X							X					
Vital Signs ^d	X	X	X	X	X			X	X	X	X				X	X				
ECOG PS	X	X						X							X					
APR-246		X	X	X	X			X	X	X	X					X				
Azacitidine ^a											X					X				
Bone marrow Biopsy and Aspiration**	X					X**													X	X
Flow Cytometry and Cytogenetics	X																		X	X
NGS Myeloid Panel ^e	X																		X	X
Correlative Studies ^f	X					X**													X	
Response Assessment																			X	X
Hematology ^g	X	X					X	X				X	X	X	X		X	X	X	X
Blood chemistry ^h	X	X					X	X				X	X	X	X		X	X	X	X
Pregnancy test ⁱ	X																			
EKG ^j	X				X			X			X				X					
Transfusion Log	X	<-----From 8 weeks prior to randomization throughout end of treatment date ----->																		
Adverse events		<-----Starting CID-14 (post 1 st dose) through 30 days post end of treatment----->																		

APR-246 will be administered as monotherapy in the lead-in phase IV over 4 days (days -14 to -10) during the Phase 1b portion only***.

For combination therapy, APR-246 is administered IV on days 1-4 of each 28 day cycle.

a: Azacitidine is administered SC or IV over 7 days starting day 4 (7 consecutive days, 4-10; or 2+5 (i.e., days 4-5 and 8-12))

b: Day 1 evaluations for subsequent cycles are to be done within 7 days prior to next cycle drug administration.

c: Full medical history will be obtained by the APP/MD at baseline for safety and eligibility purposes, though only baseline medical history items will be recorded on CRFs – this will include any issues/items from 4 weeks prior to screening date.

d: Physical exam and vital signs (including blood pressure, heart rate, respiration rate and temperature) will be completed for safety purposes though not recorded onto CRFs and items noted will be recorded as AEs where appropriate. Vitals will be collected prior to APR-246, 2 hours into infusion and at end of infusion (+/- 30 mins at all time points).

e: NGS myeloid panel will evaluate recurrent gene mutations and TP53 VAF (secondary endpoints #4-6) at study entry and every 3 cycles from peripheral blood (PB) mononuclear cells (MNC). If TP53 mutation is only present on BM analysis at screening, serial NGS myeloid panel can be performed on bone marrow MNC. Samples will be sent to Genoptix as the central laboratory for mutational analysis.

f: Correlative studies (secondary endpoints #7-8) will be performed on BM MNC during screening, day #-10 of lead in phase and every 3 cycles. If

specimen not collected (e.g. dry tap), not considered deviation.

g: Hematology including hemoglobin, WBC with differential, and platelet count.

h: Blood chemistry including sodium, potassium, BUN, glucose, ALT/AST, alkaline phosphatase, total protein, total bilirubin, albumin, creatinine, and calcium.

i: Pregnancy test; for women of childbearing potential, a negative pregnancy test (urine or serum) must be documented between Screening and first day of treatment on study. Must be documented prior to 1st dose of medication on study

j: EKG prior to initial dose of APR-246 and after infusion on day -11 of the lead in phase. EKG will be performed on day 1 and at end of infusion on day 4 of cycle 1 and then on day 1 evaluations of subsequent cycles.

Concurrent medications will not be captured on CRFs but will be reviewed with subjects in clinic at start of cycle visits to determine if they are reveal any new AEs or SAEs. For patients with documented CR or PR at disease assessment following cycle 3, hematology and blood chemistry assessments will be required for D1 of each subsequent cycle and more frequently per the discretion of the treating physician.

* All screening/baseline evaluations will be performed within 4 weeks prior to the start of APR-246 and azacitidine treatment. All assessments are to be performed on day 1 of each week. In the event that a visit or test cannot be scheduled on the exact visit day, a window of ± 7 working days is allowable.

**Bone marrow aspirate will be only be required for day #-10 in the phase 1b component of the trial. In the phase 2 component, bone marrow assessment completed within 1 month of signing consent will be accepted to fulfill screening requirement as long as it has been completed following the last MDS treatment (excluding ESAs) and there are unstained core biopsy or clot sections available for p53 immunohistochemistry.

***Lead-in phase will only be part of the Phase 1b portion of the study.

****Continuation Phase: After completing cycle 6 response assessments, subjects who have stable disease or better may continue treatment with APR-246 and azacitidine on 28 day cycles. Bone marrow biopsy and aspirate will be repeated after every 3 cycles. A CBC and CMP will be obtained at Day 1 of each cycle or more often per study investigator.

End of Cycle 6 Evaluation and End of Treatment: Subjects discontinuing treatment early should complete their end of treatment visit within approximately 28 days of their last dose of investigational product. Physical exam, vital signs, adverse event reporting, CBC, and blood chemistry and BM aspirate and biopsy with cytogenetic and NGS analysis should be performed if feasible.

Off Treatment assessment: includes best response, date of first response, date of loss of response, reason for discontinuation.

Off study CRF: vital status, date of death/last contact, transformation to AML and the date of transformation to AML if applicable.

